2 BACKGROUND AND RATIONALE

There are currently an estimated 200 EPAUs in the UK in NHS hospitals², according to the Association of Early Pregnancy Units (AEPU). EPAUs provide clinical care and support to women presenting with pain and bleeding in the first trimester of pregnancy. The National Service Framework³ recommends that EPAUs should be generally available and easily accessible, set up in a dedicated area in the hospital, with appropriate staffing and ultrasound equipment, as well as easy access to laboratory facilities. There should be direct referral access for GPs, and selected patient groups, such as women who experienced an ectopic or molar pregnancy in the past.

However, there is considerable variation between different units in the levels of access to their services and the levels of care they provide. The best configuration of EPAUs for optimal balance between cost-effectiveness, clinical, service and patient-centered outcomes remains unknown.

The recently published NICE guideline on Ectopic Pregnancy and Miscarriage (CG 154)¹ aimed to establish how different models of care within EPAUs might impact on service outcomes, clinical outcomes and women's experience of care. Fourteen studies were identified. The majority of studies (n=10)^{4,5,6,7,8,9,10,11,12,13} were conducted in the UK. Of the included studies, two were cross-sectional studies^{4,5}, four were observational studies^{6,14,15,16} that compared outcomes before and after establishment of an EPAU, and the remaining studies were descriptive^{7,8,9,10,11,12,13,17}. The quality of evidence was described as low or very low¹.

Evidence from cross-sectional studies showed that in approximately half of the units, ultrasound scans are performed by sonographers only, whilst in less than a quarter of EPAUs, the scanning is done by medical, nursing or midwifery staff^{1,4,5}. In the rest of the units, professionals from different disciplines perform ultrasound scanning. Regarding access to services, all units accept patients referred from other healthcare professionals, whilst only 51% of units accept self-referrals, and the majority of units (70%) provide a weekday service only^{1,4,5}. There is a paucity of data regarding the best indicators for clinical and service outcomes, whilst women's views and experience of care were only included in two studies^{1,11,13}.

A pilot study to test the feasibility of a large-scale study was conducted in seven EPAUs in London. The units were selected on the basis of their size, staffing configuration and access to services. As there are no auditable standards against which the EPAU service can be assessed, the main service outcomes examined were proportion of follow-up visits, proportion of non-diagnostic ultrasound scans, proportion of visits for blood tests and proportion of women admitted to hospital. A total of 3769 women were included in this pilot study. The results are shown in Table 1.

Unit	1	2	3	4	5	6	7
Follow-up attendances	26.6%	35.0%	39.8%	38.8%	36.4%	44.4%	41.1%
Non-diagnostic scans	8.0%	6.2%	8.2%	14.1%	10.6%	18.8%	30.0%
Attendances having blood tests	16.6%	11.9%	17.3%	16.2%	22.9%	28.3%	37.1%
Attendances resulting in admissions	3.9%	2.3%	4.8%	9.7%	7.9%	6.4%	9.7%
Attendances resulting in admissions for diagnostic work-up	0.0%	0.1%	0.0%	1.5%	1.4%	1.9%	2.6%

To evaluate the effects of the configuration of Early Pregnancy Assessment Units on clinical, service and patient-centered outcomes. It is hypothesized that in EPAUs with high consultant presence, the rate of hospitals admissions is lower than in units with low consultant presence.

3 OBJECTIVES

3.1 Primary Objective

To test the hypothesis that in EPAUs with high consultant presence, the rate of hospital admissions is lower than in units with low consultant presence.

3.2 Secondary Objectives

- To test the hypothesis that increased consultant presence in EPAUs improves other clinical outcomes, including number of follow-up visits, non-diagnostic ultrasound scans, negative laparoscopies and ruptured ectopic pregnancies requiring blood transfusion.
- To assess the effect of variations in opening hours and service accessibility on the overall admission rates and other clinical outcomes.
- To determine the optimal skill-mix to run an effective and efficient EPAU service.
- To examine the cost-effectiveness of different skill-mix models in EPAU.
- To explore patient satisfaction with the quality of care received in different EPAUs.
- To make evidence-based recommendations about the future configuration of EPAUs in the UK.

4 STUDY DESIGN

Multi-methods approach including: (i) cohort study of clinical outcomes, (ii) health economic evaluation including skill-mix and cost-utility model development, (iii) patient satisfaction survey, (iv) staff survey, (v) qualitative interviews with service users, and (vi) prospective hospital emergency care audit.

5 STUDY SCHEDULE

5.1 Randomisation procedure

The process for selecting the Units is described in section 8.1. There will be no randomisation of individual patients.

5.2 Definition of end of Study

The end of the study will be defined as the last 26-week/3-month follow-up visit for a participating patient.

The study will be considered closed when the last patient has reached this time-point, all data are complete and all data queries have been resolved.

6 CONSENT

Women who agree to participate will be asked by the triage (registered) nurse or midwife/research nurse or midwife/nurse sonographer/trial officer/research team lead/clinical research fellow/doctor to provide written consent before completing any study questionnaires. Members of staff who agree

to participate in the study will be asked by the local research co-ordinators to provide written consent prior to completing the staff survey.

7 ELIGIBILITY CRITERIA

7.1 Inclusion Criteria

(i) Cohort study of clinical outcomes

All pregnant women (16 years of age and over) attending Early Pregnancy Assessment Units because of suspected early pregnancy complications.

- (ii) Health economic evaluation
- (iii) Patient satisfaction survey
- (v) Qualitative interviews with service users

Pregnant women (16 years of age and over) attending Early Pregnancy Assessment Units because of suspected early pregnancy complications who agree to sign a written consent to participate.

(vi) Hospital emergency care audit
All women attending hospital emergency service because of early pregnancy complications over a period of three months.

(iv) Staff survey

All members of staff directly involved in providing early pregnancy care who agree to sign a written consent form to participate.

7.2 Exclusion Criteria

- (ii) Health economic evaluation
- (iii) Patient satisfaction survey
- (v) Qualitative study

Women who are haemodynamically unstable, in severe pain and those who decline consent to participate in the study.

8 **RECRUITMENT**

8.1 Unit recruitment

Units will be approached to participate in the study. Meetings with the lead clinician and the key members of the team will be arranged to explain the study, participant recruitment and time scale. If a unit declines participation, the next centre of similar characteristics will be approached, until an alternative centre is recruited.

8.2 Patient recruitment

(i) Cohort study of clinical outcomes

Women will be provided with the study information leaflet as they register their attendance at the clinic reception. Once they have had sufficient time to read the information leaflet they will then be approached by the triage (registered) nurse or midwife/research nurse or midwife/nurse sonographer/trial officer/research team lead/clinical research fellow/doctor and asked to participate in the study. Women who agree to participate will sign a consent form at this point.

Demographic and routine clinical data will be collected from all women attending the EPAUs. In women who consent to the study their clinical data and questionnaires will be linked using their study number. The data from women who do not consent will be anonymised and the data collection forms will not leave individual hospital premises.

(ii) Health economic evaluation

Step 1. Women who consent to the study will be asked to complete the EuroQoI-5D 5L (EQ-5D 5L) questionnaire and the Visual Analog Anxiety Scale (VAS-A) prior to their clinical assessment. They will also be asked to complete the same VAS-A at the end of their visit. In case of follow-up visits, women who consented to participate in the study will be asked to complete the VAS-A prior to and following review.

Step 2. Women who consent to the study will also be asked to complete the EQ-5D 5L questionnaire two weeks after discharge from the clinic.

Step 3. A sub-set of women, across all sites and stratified by outcome, will be asked to complete the EQ-5D-5L as well as a more detailed questionnaire about service use - the Client Service Receipt Inventory (CSRI) - 12 weeks post-discharge.

(iii) Patient satisfaction survey

Women who consent to the study will be asked to complete the Short Assessment of Patient Satisfaction (SAPS) measure as well as a condition-specific patient satisfaction questionnaire (modified Newcastle-Farnworth questionnaire) at two weeks post-discharge. Further information about the pregnancy, including the London Measure of Unplanned Pregnancy (LMUP) will also be collected.

(vi) Qualitative interviews with service users

Women who have taken part in the (iv) patient satisfaction survey and who have consented to being re-contacted in relation to a telephone interview will form the sampling frame for the qualitative interviews. A purposive, maximum-variation sample will be constructed to include women with different outcomes (e.g. ongoing pregnancy, miscarriage, ectopic pregnancy), different levels of reported satisfactions (e.g. above and below average satisfaction on SAPS), and experiences of EPAUs in different regions and with different service configurations. When re-contacted and invited for interview, women will have the opportunity to consent to an interview or to decline.

(vii) Hospital emergency care audit

Routine data for all women attending hospital emergency service due to early pregnancy complications will be collected over a period of three months at the time of site initiation. We

will collect data about the total number of attendances to EPAU and A&E departments. We will also collect data about the total number of emergency admissions, emergency operations and their outcomes, number of women receiving blood transfusions and number of admissions to intensive care units. Women will not be asked to consent to participate in this arm of the study.

Table 2 contains a summary of the different data strands of study, including types of different questionnaires and their timings.

Data strand	Data collection tool	Data source When collected		Type of data
Cohort study of clinical outcomes	CRF	All women attending the service	At site initiation until 150 women have provided complete data	Anonymised
Health economic evaluation	EQ-5D 5L Q VAS-A VAS-A EQ-5D 5L Q	Women attending the service who consent	Upon arrival at EPAU After initial clinical assessment During follow-up visit, prior to and following clinical assessment 2 weeks post-discharge	Identifiable
	CSRI Q EQ-5D 5L Q		3 months post-discharge	
Patient satisfaction survey	SAPS Q LMUP Modified Newcastle Q	Women attending the service who consent	2 weeks post-discharge	Identifiable
Qualitative interviews wih service users	Interviews	Women attending the service who consent (purposive sample of 40)	Following analysis of clinical outcomes & SAPS Q	Identifiable
Hospital emergency care audit	Routine hospital data	All women admitted to hospital	Prospective for 3 months after site initiation	Anonymised

8.3 Staff recruitment

Members of staff directly involved in providing early pregnancy care will be approached and asked to complete a modified (shortened) version of the standard NHS staff survey. We aim to recruit 200 members of staff. It will be made clear that the responses to the survey will be anonymous.

9 STATISTICAL METHODS

[name] is the study statistician who will be responsible for all statistical aspects of the study from design through to analysis and dissemination.

9.1 Sample size calculation

We plan to recruit 44 units, each contributing at least 150 patients. This will give us 90% power to detect a difference in admission of rates of 5% (8.5% vs 3.5%) between units with a low consultant presence and those with a high presence, at the 5% significance level. The results from our pilot study suggest that such a difference in admission rates is both clinically relevant and likely.

This sample size calculation is based on a simplified analysis where units are classed as having either low or high consultant presence based on a dichotomisation at the median level of consultant presence. The admission rates for the patients in the 22 units with "high" consultant presence are then to be compared to those from units with "low" consultant presence. A basic sample size calculation (that assumes no clustering) suggests that we require 946 patients in total (or 22 per unit). However, assuming a moderate level of clustering (ICC = 0.04) we would require 150 patients per Unit. Data collection for each unit will be for minimum seven days to ensure weekday/weekend variation is captured.

For the subsidiary data strands, the anticipated response rates are as follows:

(ii) Health economic evaluation

In the absence of prior knowledge of the expected values and standard deviations of costs and effects (in this case, QALYs) it is not possible to formally estimate a required response rate. Therefore, we have taken a pragmatic approach to determining the number of resource use questionnaires to collect. Our aim is to balance the collection of sufficient data to make inferences about cost-effectiveness against the burden on women of being asked to complete data collection forms shortly after the loss of a pregnancy.

Questionnaires will be sent to randomly chosen women, selected from those who have given prior consent for further contact. The sample will be stratified using the same criteria as used to select participating EPAUs. We anticipate that 320 completed questionnaires will provide sufficient data.

An algorithm and approach to sampling similar to that used to select units for participation in the study, will be used to select women to be approached to complete the resource use questionnaire. The key factors used to sample will be consultant presence (at four levels), weekend availability and number of patients attending. Each stratum of each key factor will be equally represented. That is, 80 women will be in stratum 1 for consultant presence, 80 will be in stratum 2, and so on. Likewise, 160 women will be in stratum 1 for weekend opening and 160 will be in stratum 2, and similarly for number of patients attending a unit. Women will be approached to complete the resource use questionnaire until we achieve 320

responses balanced across factors and strata.

In order to accurately capture the workforce resources needed to run each EPAU, we will prospectively collect data on members and grades of staff involved in providing care as well as the time spent providing this care. Consultant presence will be collected prospectively for each session/day that data will be collected for (i.e. a record of whether a consultant is physically present in the unit reviewing patients will be collected for every session for which we are collecting data).

(iii) Patient satisfaction survey

Our study population will include 6600 women (150 x 44 units, see above). If our response rate is 30%, then a 95% confidence interval (for a yes/no question) will have a margin of error of at most 2.2%. If the response rate is just 10%, then the error will be at most 3.8%.

(iv) Staff survey

We expect that there will be approximately 200 staff members in the sample of 44 units. If our response rate is 50%, then a 95% confidence interval (for a yes/no question) will have a margin of error of at most 10%.

(v) Qualitative interviews with service users

Forty interviews will be carried out with EPAU service users. This calculation is based on the needs of the intended maximum variation sample^{18,19} (enabling representation by region, pregnancy outcome, and reported level of satisfaction) and will provide a wealth of qualitative data for analysis.

(vii) Hospital emergency care audit

Results from the pilot study and the initial clinician survey showed that the average number of women reviewed in different EPAUs across the country is 105 per week. We are planning to collect hospital statistics data over three months, which should provide us with sufficient numbers to have enough power to detect significant differences in rare outcomes such as the proportion of negative laparoscopies, transfusion rates and ITU admissions.

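### The patient-survey margins of error (at most 2.2% and 3.8%) hold only if women respond independently, while the same section assumes clustering within the same 44 units

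*Protocol*

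**What the plan says.** Section 9.1, under the patient satisfaction survey, starts from the cohort: "Our study population will include 6600 women (150 x 44 units, see above"). It then gives two precision statements for a yes/no item. At a 30% response rate, "a 95% confidence interval (for a yes/no question) will have a margin of error of at most 2.2"%. For a lower response, "If the response rate is just 10%, then the error will be at most 3.8"%. It mentions no design effect, ICC or independence assumption.

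Earlier in section 9.1 the primary calculation treats women in the same unit as correlated. A requirement of 946 women in total (22 per unit) without clustering is raised because "assuming a moderate level of clustering (ICC = 0.04) we would require 150 patients per Unit". That ICC is stated for admission rates. The protocol gives none for satisfaction items.

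Three other places bear on the point. Section 1 says that, because units vary, women are likely to have different experiences of care. Section 3.2 sets an objective of exploring satisfaction in different EPAUs. Section 9.3.2 lists patient satisfaction among the secondary outcomes to be analysed along the lines of the primary analysis, which section 9.3.1 defines as a hierarchical model with patients clustered within EPAUs.

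**The concern.** The survey respondents are a subset of the cohort women, attending the same 44 units. Section 9.1 corrects for within-unit correlation in one calculation and leaves it out, without comment, in the next one on the same sample. Satisfaction with a unit's care is an outcome for which between-unit variation is to be expected, and the protocol says as much in section 1. An ICC of zero for survey items is therefore at odds with the study's own premises.

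The phrase *at most* turns the figures into upper bounds. They are upper bounds over the true proportion (the worst case is 50%), but only when the ICC is zero.

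What is at stake is the precision claimed for the survey, including the reassurance it offers if response falls to 10%. The independence calculation also overstates what a better response rate buys. More respondents from the same 44 units do little to reduce the between-unit part of the error.

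**Working it through.** **Inputs**
- Population 6600 = 150 × 44 (section 9.1, patient satisfaction survey).
- Response rates 30% and 10% (same place).
- 95% confidence, z = 1.96 (same place).
- Proportion 0.5, the worst case implied by *at most*.
- ICC 0.04 (section 9.1, primary calculation, for admissions). Its use for survey items is an assumption, so a range is shown.
- Equal response across units (assumption).

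**1. Reproduce the stated figures.** Margin under independence = z × √(0.25/n).
- 30% response: n = 6600 × 0.30 = 1980; 1.96 × 0.5/√1980 = 2.20%.
- 10% response: n = 6600 × 0.10 = 660; 1.96 × 0.5/√660 = 3.81%.

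Both match. A finite population correction with N = 6600 would give 1.84% and 3.62%, which do not match. The stated figures are therefore plain independent-sample margins.

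**2. Confirm that the primary calculation does use clustering.** Comparing 8.5% with 3.5% at 90% power needs 473 per group, 946 in total, as stated. With 44 units and ICC 0.04, the number m per unit must satisfy 44m/(1 + (m − 1) × 0.04) = 946. So m = 946 × 0.96/(44 − 946 × 0.04) = 147.4, consistent with the stated 150.

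**3. Apply the same design effect to the survey.** DEFF = 1 + (m − 1) × ICC, and clustered margin = independent margin × √DEFF.
- 30% response: m = 1980/44 = 45; DEFF = 1 + 44 × 0.04 = 2.76; margin = 2.20% × 1.661 = 3.66%; effective n = 1980/2.76 ≈ 717.
- 10% response: m = 660/44 = 15; DEFF = 1 + 14 × 0.04 = 1.56; margin = 3.81% × 1.249 = 4.76%; effective n = 660/1.56 ≈ 423.

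These are 66% and 25% wider than stated.

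**4. Sensitivity to the ICC**

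| ICC | 30% response | 10% response |
|---|---|---|
| 0 (as stated) | 2.20% | 3.81% |
| 0.01 | 2.64% | 4.07% |
| 0.02 | 3.02% | 4.32% |
| 0.04 | 3.66% | 4.76% |
| 0.05 | 3.94% | 4.97% |

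**5. Value of a higher response rate.** Going from 10% to 30% response cuts the stated margin by 1 − 2.20/3.81 = 42%. At ICC 0.04 it cuts the margin by 1 − 3.66/4.76 = 23%.

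**The case against.** **The ICC is borrowed.** The 0.04 was assumed for admissions, and nothing in the protocol gives a value for survey items. This stands. It governs the size of the shortfall but not its direction, which is why a range is needed rather than a single replacement figure.

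**The simple design effect may be too large.** Section 9.1 refers to an algorithm for selecting units, with consultant presence, weekend availability and patient numbers as key factors. An estimate that used this stratification would remove some between-unit variation. Section 2 puts the number of UK units at about 200, so 44 units are 22% of them. If those units are the target, the between-unit part shrinks by 1 − 0.22 = 0.78. The variance factor is then 0.96 + 45 × 0.04 × 0.78 = 2.36 at 30% response and 0.96 + 15 × 0.04 × 0.78 = 1.43 at 10%, giving margins of about 3.4% and 4.6%. Unequal response across units would push the other way. So 3.7% and 4.8% are approximate, but both adjusted figures still exceed the stated bounds.

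**Many items will not sit at 50%.** At ICC 0.04 the stated margins are still met for proportions of about 10% or less, or 90% or more, at 30% response, and of about 20% or less, or 80% or more, at 10% response. That is true, but a bound described as a maximum has to hold at 50%.

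**Under-coverage does not follow.** A reader might infer that the survey's confidence intervals will be computed naively and cover well below 95%. The protocol does not support that. The margins are planning figures in a sample-size section and prescribe no method for computing intervals. Sections 9.3.1 and 9.3.2 plan a hierarchical analysis for patient satisfaction, and section 12 leaves detail to an analysis plan. Those sections do not expressly address simple descriptive proportions, but nothing says these will ignore clustering.

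**It drives no design decision.** Survey size follows from the cohort, the objective is exploratory, and no precision target is set that the wider margins would miss. This also stands, and it limits the importance of the point.

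**Conclusion.** The stated margins are computed correctly, but under an unstated independence assumption that conflicts with the clustering assumed elsewhere in section 9.1 and with the between-unit variation expected in section 1. As upper bounds they fail for any positive ICC at a proportion of 50%; an ICC of only 0.01 is enough to exceed both.

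Carrying over the ICC of 0.04 with equal response across units, the worst-case margins are about 3.7% instead of 2.2% and 4.8% instead of 3.8%. Because that ICC belongs to a different outcome, these figures should be read with the range for ICCs of 0.01 to 0.05: about 2.6% to 3.9% at 30% response and 4.1% to 5.0% at 10%.

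The fault lies in a precision statement for a subsidiary strand. It is not an arithmetic slip, it does not show that the planned satisfaction analysis is invalid, and it leaves the primary sample size untouched.

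**What to change.** Replace the two margin statements in section 9.1 (patient satisfaction survey) with wording such as:

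> For a yes/no item with a true proportion of 50%, assuming equal response across 44 units and an ICC of 0.04 carried over from the admission outcome, the 95% margin of error is about 3.7% at 30% response (45 per unit, design effect 2.76) and 4.8% at 10% response (15 per unit, design effect 1.56). For ICCs from 0.01 to 0.05 the margins are about 2.6% to 3.9% and 4.1% to 5.0% respectively.

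An upper-bound phrase may stay if it is tied to the stated ICC.

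Add one sentence saying that intervals for any simple descriptive survey proportions will allow for clustering by EPAU, in line with the hierarchical analysis already planned in sections 9.3.1 and 9.3.2. No new model is needed for the satisfaction outcome itself.

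The cost is a less favourable precision figure. No extra respondents, units or data items are required.
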